TITLE:

Clinical Outcomes Associated With the Use of ViviGen® for the Treatment of Lumbar Degenerative Disc Disease

NCT03733626

Approval date: 10/18/2019

Study Protocol and Statistical Analysis Plan

Clinical Outcomes Associated with the use of ViviGen® in Conjunction with Posterolateral Fusion for the Treatment of Lumbar Degenerative Disc Disease

[name]. (First Author)

Department of Orthopaedic Surgery
William Beaumont Hospital
[name]
[name]
[contact]

[name].

Department of Orthopaedic Surgery
William Beaumont Hospital
[name]
[name]
[contact]

[name].* (Corresponding Author)

Department of Orthopaedic Surgery
William Beaumont Hospital
[name]
[name]
[contact]

[name].

Department of Orthopaedic Surgery
William Beaumont Hospital
[name]
[name]
[contact]

*For Correspondence:

[name]. Director, Orthopaedic Research Laboratory
Department of Orthopaedic Surgery [name]
Office: [contact] [contact] [contact]

Introduction

DePuy Synthes, Inc. is proposing a prospective randomized interventional outcomes study of clinical safety and fusion rates in subjects who have received standard-of-care one or two-level posterolateral lumbar fusion surgery with instrumentation using ViviGen® Cellular Bone Matrix on-label for the treatment of degenerative disc disease.

Background and Significance

Nearly half of the estimated 500,000 bone grafting procedures performed annually in the United States involve spine fusion.¹ Traditionally, autologous bone grafts are used to repair damaged bone caused by trauma, infection, malignancy, degenerative disease and congenital deformity. However, harvesting of bone autograft is an invasive procedure that can lead to significant donor site morbidity.²

Bone graft substitute (BGS) materials offer an alternative to autograft bone capable of supporting new bone growth, while avoiding or minimizing the frequent co-morbidities associated with autograft harvest from the iliac crest.³⁻⁵ Allograft bone has been used successfully for more than two decades as a first-generation alternative to autograft bone. While traditional processed allograft bone can be difficult to shape, shows variable resorption characteristics, and variable biological activity, ViviGen® Cellular Bone Matrix has addressed these issues in their product. While containing all the properties required for bone formation, it additionally has a consistency that allows it to hold shape in a putty-like consistency.⁶ ViviGen® Cellular Bone Matrix can be molded into a specific form that allows proper placement, positioning and formation during posterolateral lumbar fusion.⁶

Description of ViviGen®⁶

ViviGen® is manufactured by DePuy Synthes, Inc. (West Chester, Pennsylvania). ViviGen® Cellular Bone Matrix is comprised of cryopreserved viable cortical cancellous bone matrix and demineralized bone. ViviGen® Cellular Bone Matrix is a Human Cells, Tissues, and Cellular and Tissue-based Product (HCT/P) as defined by the U.S. Food and Drug Administration in 21 CFR 1271.3. ViviGen® Cellular Bone Matrix is processed from donated human tissue, resulting from the generous gift of an individual or his/her family.

ViviGen® Cellular Bone Matrix contains all of the properties required for bone formation being that it is osteoconductive, osteoinductive and osteogenic. Safety of ViviGen® Cellular Bone Matrix is defined by every lot is aseptically processed and final product is tested for sterility using USP standards. Packaging and handling is beneficial in that all four sizes of ViviGen® Cellular Bone Matrix will thaw in less than 5 minutes, which is vital for cell viability, in that the ported pouch allows for the quick and efficient removal of the cryopreservation media and rinsing solutions. ViviGen® Cellular Bone Matrix maximizes cell viability by modes of processing that is focused on protecting viable lineage committed bone cells from recovery to implantation.

Objective

The objective of this study is to perform a prospective, randomized, controlled clinical trial to compare radiographic fusion rates and patient reported outcomes, including pain and function preoperatively and postoperatively, using Depuy ViviGen® Cellular Bone Matrix mixed with

cortical/cancellous allograft in conjunction with an approved Depuy Synthes pedicle screw system compared to autograft mixed with cortical/cancellous allograft in conjunction with the same DePuy Synthes pedicle screw system used for a one or two- level posterolateral lumbar fusion.

Methodology

Study Design

This is a prospective randomized, non-blinded, controlled study. Patients with a diagnosis of degenerative disc disease and/or up to grade I spondylolisthesis and planning to undergo a 1- or 2-level instrumented posterolateral lumbar fusion surgery between L1-S1 will be screened. If eligible and the subject meets all the inclusion criteria and none of the exclusion criteria, the subject will be approached about study participation by the surgeon. If the subject agrees to participate, the consent process will be initiated by the study coordinator. Once the patient has been consented; data including medical history, neurological exam, patient questionnaires (VAS, ODI, SF-36) will be collected. Randomization will occur once a surgery date has been scheduled so the appropriate instrumentation can be boarded accordingly. A randomization envelope will reveal randomization treatment group. The envelopes will be generated in a 1:1 fashion and be randomly allocated to an assigned study identification number. Subjects will be randomized to either: 1) treatment arm where the investigator will use an FDA approved/cleared DePuy Synthes spinal pedicle screw system with ViviGen® Cellular Bone Matrix mixed with cortical/cancellous allograft or the 2) control arm where the investigator use the same DePuy Synthes spinal pedicle screw system with local autologous bone graft mixed with cortical/cancellous allograft. Both treatment groups represent standard of care lumbar fusion surgeries using two types of bone graft options to create the arthrodesis as comparators.

Once the lumbar fusion surgery has taken place as planned; data will be collected regarding the surgery performed, including operative time, amount of bone graft used, spinal system used, length of hospital stay, and adverse events/complications.

Study subjects will be followed up at 6-weeks, 3-months, 6-months, and 12-months postoperatively at the private practice or clinic. During these routine (standard of care) postoperative visits, subjects will complete questionnaires (VAS, ODI, SF-36, patient satisfaction) and have neurological exam (lumbar spine exam, see appendix 1) completed by the investigator. Adverse events related to device and/or procedure will be evaluated as each postoperative visit. AP and lateral x-rays will be performed at all visits with flexion and extension x-rays added at baseline, 3-months, 6-months, and 12-months. A CT scan of the lumbar spine will be performed during the 12-month postoperative time frame at the Beaumont-RO Imaging Center. Radiographic analysis will be performed and evaluated for fusion status as evidenced by bony bridging, presence of radiolucency, and development of pseudoarthrosis at each follow-up visit.

This study design reflects the current standard of care for lumbar spinal stenosis, degenerative disc disease and lumbar degenerative spondylolisthesis. Lumbar fusion surgery using pedicle screw fixation with autograft and allograft bone grafting options is treatment of choice after conservative (non-surgical) therapies have been implemented and failed.

Statistical Analysis

The sample size will consist of 40 patients; 20 in each treatment arm. The primary hypothesis is that the probability of achieving fusion using ViviGen bone graft is not clinically inferior to using autograft and allograft in lumbar fusion at 12-months post-surgery. Using a one-sided test and fusion rate of 86%, there is a 0.80 probability of 0.80 of finding a difference for 60 patients. A 10% dropout rate was considered. Forty patients may result in low statistical power; however, this may be increased by 10 in each arm once enrollment has obtained and if needed, and upon agreement with study sponsor. Enrollment of 40 reflects the current allotted grant/budget per the study sponsor for this project.

There are other studies that analyzed demineralized bone matrix in two-year fusion outcomes for lumbar spinal fusions that used a similar size population (range between 13 and 28 patients) to the proposed enrollment for this study, as demonstrated in *Vaccaro et al (2007)* and *Kang et al (2012)*. Power calculation for the primary outcome of bone fusion was obtained using PASS 15. An 86% fusion rate (Kang et al) was assumed with a 10% dropout rate for both arms.

Secondary endpoints (VAS, ODI, SF-36, neurological status, and fusion) will be quantified to detect changes longitudinally from baseline through 12-months post-surgery.

Study Population and Inclusion/Exclusion Criteria

Patients with a diagnosis of spinal stenosis, degenerative disc disease and/or up to grade I spondylolisthesis and planning to undergo a 1 or 2-level instrumented posterolateral lumbar fusion surgery between L1-S1 will be asked to participate in the study. If eligible, the consent process will be initiated by the study coordinator

A subject may be included if the following criteria are met:

1. ≥ 18 years of age
2. Able to provide consent
3. Is undergoing standard of care one or two-level instrumented posterolateral fusion at the level between L1-S1
4. Has diagnosis of spinal stenosis, degenerative disc disease and/or up to Grade 1 spondylolisthesis
5. Requires decompression at intended fusion level (multi-level decompression allowed L1-S1)
6. Has failed 6-weeks or more of conservative, non-operative treatment
7. Has back and/or radicular lumbar symptoms with ODI (Oswestry Disability Index) score of ≥ 30 preoperatively.

A subject will be excluded if any of the following criteria are met:

1. Any prior lumbar fusion surgery
2. Requires fusion of more than two levels
3. Requires an interbody fusion based on relevant diagnosis and factors (such as foraminal stenosis, degree of spondylolisthesis, spinal deformity, disc space collapse, and subject's age) as determined by investigator
4. BMI > 40

5. Active systemic infection or infection at operative site
6. History of an osteoporotic fracture and/or vertebral body fracture
7. Is currently being treated with chemotherapy, radiation, immunosuppression or chronic steroid therapy
8. History of osteoporosis, osteopenia, or osteomalacia that would contraindicate spinal surgery
9. Psychological or physical condition in the opinion of the investigator that would interfere with subject self-assessments
10. History of neurological condition in the opinion of the investigator that may affect lumbar function and pain assessments
11. Subjects with a history of cancer must be disease free for at least 3 years
12. Pregnant, or plans on becoming pregnant

Intervention

Treatment arm/group: 20 subjects undergoing open, one or two-level instrumented posterolateral lumbar fusion surgery using ViviGen Cellular Bone Matrix mixed with cortical/cancellous allograft and DePuy Synthes pedicle screw system.

Control arm/group: 20 subjects undergoing open, one or two-level posterolateral lumbar fusion surgery using local autograft mixed with cortical/cancellous allograft and DePuy Synthes pedicle screw system.

Data and Safety Monitoring

The PI and study team (including sub-investigators, clinical research manager) will be responsible for data and safety monitoring. All adverse events will be reviewed to determine relatedness to the product and reported to sponsor as necessary (if related to product and unanticipated according to risk profile). The data will be reviewed for maintenance of confidentiality and integrity as well as the data collection process. The data and safety review will take place every six months from the date of the first patient enrolled into the study or after every ten patients enrolled whichever comes first.

Adverse Events

Relevant adverse events (those related to the study device, the surgical procedure, or the lumbar spine) will be recorded in this study. All adverse events will be reviewed for relatedness and expectedness by the PI on a case by case basis and per Data and Safety Monitoring guidelines.

Protocol Deviations

The investigators are responsible for documenting all protocol deviations, including an explanation for why the deviation occurred. All protocol deviations will be recorded and submitted to the IRB per policy.

Outcomes

Primary Endpoint

IRB NUMBER: 2018-158

IRB APPROVAL DATE: 10/18/2019

- Successful lumbar fusion as measured by CT scan and flexion/extension x-rays at 12-months; as evidenced by bony bridging, presence of radiolucency, no development of pseudoarthrosis

Secondary Endpoints

- Improvement in patient reported outcomes as measured by VAS (\geq 2-point improvement), ODI (\geq 15-point improvement), SF-36 (\geq 15-point improvement) from baseline to 12-months.
- No new or worsening neurological (motor and sensory) deficit as compared to baseline through 12-months. No revision surgery and/or development of pseudoarthrosis by month 12.
- No occurrence of adverse events related to device by month 12.

Subject Screening and Enrollment

Patients who have already planned a decompressive lumbar laminectomy and fusion surgery will be approached about potential study participation. If the patient wishes to proceed with study participation, the study coordinator will go through the informed consent process. After the consent process has been completed, the subject will be further screened for eligibility and given the subject questionnaires to complete.

Screen Failures

If the subject does not meet all inclusion criteria or meets one of the exclusion criteria after signing consent, then the subject will be considered a screen failure and therefore, not enrolled into the study. The subject will also be considered a screen failure and not enrolled in the study if there is a change in surgical treatment based on the surgeon's observations and best practice intraoperatively.

Withdrawals

A subject who withdraws consent prior to study completion will be removed from the study and no longer followed. The surgery, instrumentation, and bone grafts are FDA approved and cleared and considered standard of care. The subjects may follow-up as needed and per standard of care at their own discretion if they decide to no longer participate in the study.

The reasons for voluntary withdrawal or discontinuation of study subjects will be documented. If during the course of the clinical study, a study subject is non-responsive to attempts to schedule follow-up visits, communication methods such as phone calls, emails, mail, or other means as appropriate in an attempt schedule an appointment or determine if the subject has moved, died, or otherwise become lost to follow-up.

Summary and Rationale of Proposed Study

The purpose of this study is to collect on-label safety and efficacy data where ViviGen® Cellular Bone Matrix is applied to posterolateral lumbar fusion with DePuy Synthes pedicle screw system. It is expected that this study will contribute to the compilation of clinical data required

to demonstrate the ability of ViviGen® Cellular Bone Matrix to promote safe, effective and timely spine fusion in patients who undergo posterolateral lumbar fusion surgery. The results of this study will lead to further analysis (i.e. comparison to historical data of other marketed bone graft products, as well as, to local bone alone).

References

1. Boden SD. Overview of the biology of lumbar spine fusion and principles for selecting a bone graft substitute. *Spine* 27, S26-S31 (2002).

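### Randomisation is not stratified by planned one- or two-level fusion and no analysis accounts for level; this leaves a modest, avoidable chance error in the fusion comparison at 20 per arm

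*Combined protocol and SAP*

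**What the plan says.** Inclusion criterion 3 admits a patient who "Is undergoing standard of care one or two-level instrumented posterolateral fusion at the level between L1-S1". The Intervention section repeats the mix for the experimental arm ("Treatment arm/group: 20 subjects undergoing open, one or two-level instrumented posterolateral lumbar fusion surgery") and describes the control arm in matching terms.

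Under Study Design, the allocation rule is: "The envelopes will be generated in a 1:1 fashion and be randomly allocated to an assigned study identification number". No stratification factor, block or minimisation scheme is described. The same section delays randomisation until a surgery date is fixed, so the planned number of levels should be known before the envelope is opened.

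Under Statistical Analysis, "The sample size will consist of 40 patients; 20 in each treatment arm", and "this may be increased by 10 in each arm once enrollment has obtained and if needed", subject to the sponsor's agreement. The hypothesis is that "the probability of achieving fusion using ViviGen bone graft is not clinically inferior to using autograft and allograft". No adjustment for level and no analysis by level is mentioned. The only fusion rate given is 86%, attributed to a cited study whose title (reference 8) restricts it to single-level fusions. The primary endpoint does not say how success is counted in a patient with two fused levels.

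**The concern.** Number of levels is a fixed feature of the planned operation and could plausibly affect whether a patient is counted as fused. If success requires every treated level to fuse, a two-level patient has two ways to fail. When the arms differ in their share of two-level patients, part of the observed fusion difference then reflects case mix rather than graft.

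With 20 per arm such a difference can arise by chance. The plan handles it neither at allocation nor in the analysis. At stake is the reading of a single small, non-blinded non-inferiority comparison that the protocol itself says may have low power: a visible imbalance in levels would be an easy objection to the result in either direction.

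**Working it through.** **The plan's own figure.** "Using a one-sided test and fusion rate of 86%, there is a 0.80 probability of 0.80 of finding a difference for 60 patients", and "A 10% dropout rate was considered". This cannot be reproduced because no margin and no alpha are stated. Solving backwards with 86% in both arms, 60 patients fit a margin of about 22 points (one-sided alpha 0.05, 30 per arm) or 23 points (27 evaluable per arm), and 25-26 points at alpha 0.025. No planned figure concerns level, so the size of the issue has to be worked out from assumptions.

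**Inputs.** From the documents: 20 per arm, and an 86% fusion rate. Assumed: an exact 20/20 split; a two-level share of 20-50%, that is K = 8 to 20 of 40 patients; and, for the shift, 86% per level, independent levels and both levels required to fuse.

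**Step 1: chance of imbalance.** With K two-level patients in all, the number x in one arm is hypergeometric, P(x) = C(20,x)·C(20,K−x)/C(40,K), and the arms differ by |2x − K|.

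For K = 8, a difference of at least 4 means x ≤ 2 or x ≥ 6:

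2 × [125,970 + 20×77,520 + 190×38,760] / 76,904,685 = 18,081,540 / 76,904,685 = 0.235.

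A difference of at least 6 means x ≤ 1 or x ≥ 7:

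2 × [125,970 + 1,550,400] / 76,904,685 = 0.044.

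| Two-level patients of 40 | Differ by ≥ 2 (10 points) | Differ by ≥ 4 (20 points) | Differ by ≥ 6 (30 points) |
|---|---|---|---|
| 8 (20%) | 69.5% | 23.5% | 4.4% |
| 12 (30%) | 73.1% | 30.1% | 8.2% |
| 16 (40%) | 74.8% | 33.3% | 10.5% |
| 20 (50%) | 75.2% | 34.3% | 11.3% |

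The mean absolute imbalance is 10-12.5 points. These probabilities cover both directions; the chance that one named arm has the excess is half of each.

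Sensitivity:
- At a 10% share (K = 4), a difference of at least 4 has probability 10.6%.
- If K is not fixed and the arm counts are independent binomials, the 20-50% range becomes 16-27% for at least 4 and 3-8% for at least 6. It is lower because with K fixed and even the difference can only be even.
- At 30 per arm, a 20-point imbalance (at least 6 patients) has probability about 10-20% with K fixed and 7-16% with binomial counts.

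**Step 2: shift in the fusion difference.** Shift = imbalance × gap between one- and two-level success.
- Two-level success = 0.86² = 0.7396; gap = 0.86 − 0.7396 = 0.1204.
- 20-point imbalance: 0.20 × 0.1204 = 0.024, or 2.4 points.
- 30-point imbalance: 0.30 × 0.1204 = 0.036, or 3.6 points.
- For other assumed gaps of 5 to 25 points, a 20-point imbalance shifts the difference by 1 to 5 points. Positive correlation between levels would shrink the gap.

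**Step 3: against sampling error.** SE = √(2 × 0.86 × 0.14 / 20) = 0.110. The shifts are 2.4/11.0 = 0.22 and 3.6/11.0 = 0.33 of one standard error, or 0.5 and 0.7 of one patient in an arm of 20. If the Step 2 assumptions also set the overall rate, it falls to 0.836 at a 20% share and 0.800 at 50%. The SE rises to √(2 × 0.836 × 0.164 / 20) = 0.117 and √(2 × 0.800 × 0.200 / 20) = 0.127, so the ratios are slightly smaller.

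**Step 4: what stratifying gains.** Holding the overall rate at 86%, the stratified SE is √(2 × [(1−s)·p₁(1−p₁) + s·p₂(1−p₂)] / 20), where s is the two-level share.
- s = 0.2, gap 10 points (0.88 and 0.78): √(2 × 0.1188 / 20) = 0.109.
- s = 0.5, gap 25 points (0.985 and 0.735): √(2 × 0.1048 / 20) = 0.102.

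The SE therefore falls from 0.110 to about 0.102-0.109, and the required sample size hardly changes. With blocks of 4 as an illustration, the arms could differ by at most 2 patients within each level stratum.

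**The case against.** Unstratified randomisation is valid. Chance imbalance averages zero over randomisations and is already part of the sampling error of an unadjusted comparison, so overall type I error is not inflated. The shift is at most about a third of a standard error in the main scenario, and small beside the 22-26 point margins that would fit 60 patients. Blocks within small strata of an open-label, single-site trial make the next allocation easier to guess, which trades a small random error for a possible systematic one. All of this stands, and it limits the point to a modest improvement.

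A reader might go further and infer that a sizeable imbalance is likely, that two-level cases are harder to fuse, and that the imbalance could create or hide non-inferiority. The documents do not support this:
- Only a 2-patient difference is more likely than not.
- No section says that two-level cases fuse less often, and the success rule for such patients is undefined.
- Without a stated margin, no claim about reversing the conclusion can be tested.
- Nor can a shortage of local bone at two levels be inferred. Decompression is required at the intended fusion level and may span several levels, and the local bone is mixed with allograft.

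What remains is that the trial is run once and will be read with whatever imbalance occurred. Neither the design nor the analysis deals with it, although the factor is available in advance.

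**Conclusion.** The point holds as a low-cost design improvement, not as a flaw that invalidates the comparison. Both fusion lengths are eligible, allocation is not described as stratified by level, and no planned analysis uses level. A 20-point imbalance has roughly a one-in-four to one-in-three chance, and a 30-point imbalance about one in nine or less, if 20-50% of patients are two-level and the split is 20/20. The consequence is a shift of about 2.4 or 3.6 points beside a standard error of about 11. That shift rests on a per-level rate of 86%, independent levels and a rule that both must fuse, none of which the plan states. The missing margin and alpha, enrolment of 40 against the 60 needed for the stated power, and the use of a single-level rate for a mixed population are larger problems in the same plan.

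**What to change.** Prepare two envelope series, one for planned one-level and one for planned two-level fusion, each 1:1 in permuted blocks of varying, concealed size. Record the planned number of levels before the envelope is opened, and keep the patient in that stratum for analysis whatever is done in theatre. Stratify the primary fusion comparison by this factor, for example with a Mantel-Haenszel risk difference, because stratified allocation gains precision only if the analysis uses it. If enrolment has begun, leave the envelopes alone and pre-specify the level-stratified analysis. In either case, state how fusion success is counted for a two-level patient.

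The cost is a new envelope list and a few sentences in the protocol, with no extra patients or procedures. Two downsides should be accepted openly. Blocks in a small open-label single-site trial are partly predictable, which varying and concealed block sizes reduce but do not remove. Incomplete final blocks in the two strata may also leave the arms slightly off 20/20.

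### The primary non-inferiority hypothesis on 12-month fusion has no margin and no alpha, so the plan cannot decide it; the only power figure cannot be checked and is not for the 40 patients planned

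*Combined protocol and SAP*

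**What the plan says.** The Statistical Analysis section states the primary hypothesis as one of non-inferiority: the probability of fusion with ViviGen "is not clinically inferior to using autograft and allograft in lumbar fusion at 12-months post-surgery".

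The power statement follows directly: "Using a one-sided test and fusion rate of 86%, there is a 0.80 probability of 0.80 of finding a difference for 60 patients". The section adds that "Power calculation for the primary outcome of bone fusion was obtained using PASS 15", and that an 86% fusion rate taken from a cited study "was assumed with a 10% dropout rate for both arms". It does not name the PASS procedure or test, and it gives no margin, alpha or confidence level. None of these appears in the Outcomes section or the Study Synopsis either.

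The enrolment is smaller than the number in the power sentence: "The sample size will consist of 40 patients; 20 in each treatment arm". The plan says so openly: "Forty patients may result in low statistical power". It gives the budget as the reason and allows that "this may be increased by 10 in each arm once enrollment has obtained and if needed, and upon agreement with study sponsor". No power is given for 40.

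The Study Design section describes the trial as non-blinded, with radiographs "evaluated for fusion status as evidenced by bony bridging, presence of radiolucency, and development of pseudoarthrosis at each follow-up visit".

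**The concern.** A non-inferiority hypothesis is decided by comparing a confidence limit with a margin. Being one-sided fixes the direction of the test, not its error rate, and the notion of clinical inferiority is never given a number. With both quantities open, there is no rule by which the primary result counts as a success or a failure, and two analysts could reach opposite conclusions from identical data.

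The power sentence does not fill the gap. It speaks of finding a difference and gives a single fusion rate. If 86% applies to both arms there is no difference to find, so the calculation needed further inputs that are not reported. It also describes 60 patients rather than the planned 40.

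The trial is open-label and fusion is read at every visit. A margin or alpha chosen late could therefore be chosen with knowledge of how the arms compare, and nothing in the text rules that out.

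**Working it through.** **Inputs from the plan (Statistical Analysis section):** fusion rate 86%, one-sided test, 10% dropout, power 0.80 at 60 patients, planned enrolment 40. Allocation is 1:1 (Study Design). Evaluable after dropout: 40 x 0.9 = 36 (18 per arm) and 60 x 0.9 = 54 (27 per arm).

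**Assumptions, because the plan gives no figure:** one-sided alpha 5% or 2.5%; margins of 10 to 25 points; a true rate of 86% in both arms.

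**1. Can the 0.80 be reproduced?** Not from the stated inputs; one can only solve for the margin that each alpha would imply. By normal approximation, margin = (z_alpha + z_0.80) x sqrt(2 x 0.86 x 0.14 / n), with z_0.80 = 0.842. The plan does not say whether the 60 is before or after dropout, so both are shown.

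- n = 30 per arm: the square root is 0.0896. At 5%, (1.645 + 0.842) x 0.0896 = 0.223. At 2.5%, (1.960 + 0.842) x 0.0896 = 0.251.
- n = 27 per arm: the square root is 0.0944. At 5%, 0.235. At 2.5%, 0.265.
- Smallest margin with exact Farrington-Manning score power of at least 0.80, at n = 30 / 27: 0.231 / 0.243 (5%) and 0.264 / 0.277 (2.5%).

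The implied margin is thus about 22 to 28 points.

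Other readings do not settle it. As a superiority test with 30 per arm at one-sided 5%, 0.80 needs 86% against about 58%; 86% against 99.9% reaches only 0.68. If the repeated 0.80 is read as a ratio margin on the log scale, power is 0.805, but only with alpha 10% and 30 evaluable per arm, and the plan states neither that alpha nor that scale.

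**2. Does the missing alpha change a conclusion?** Score lower limits for ViviGen minus control, 18 per arm:

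| Fused, each arm | One-sided 5% | One-sided 2.5% |
|---|---|---|
| 16/18 | -19.5 points | -23.8 points |
| 18/18 | -13.1 points | -17.6 points |

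With 16/18 in each arm, a 22-point margin is met at 5% and missed at 2.5%. A 15-point margin is missed at both.

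**3. Power at the planned size.** Exact score-test power, 86% in both arms:

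| Margin | 36 evaluable, 5% | 54 evaluable, 5% | 36 evaluable, 2.5% | 54 evaluable, 2.5% |
|---|---|---|---|---|
| 10 points | 0.19 | 0.26 | 0.11 | 0.17 |
| 15 points | 0.36 | 0.45 | 0.23 | 0.31 |
| 20 points | 0.52 | 0.67 | 0.36 | 0.50 |
| 25 points | 0.66 | 0.81 | 0.52 | 0.71 |

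At the margins implied in step 1, exact power with 40 enrolled is about 0.52 to 0.66.

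**4. Precision if estimation replaces the test.** Half-width of the 95% CI by normal approximation: 1.96 x sqrt(2 x 0.86 x 0.14 / 18) = 0.227, and with 27 per arm 0.185. That is roughly 23 and 19 points either way.

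**The case against.** The best defence is that this is a small, budget-limited study that does not hide its limits. It says 40 may be too few, explains why and provides for 60. The synopsis objective is only to evaluate fusion, and the margin may well sit in the PASS file. The candour about size stands: the missing power figure for 40 would on its own be a disclosure gap. But admitting low power does not supply a decision rule, and a margin held in a software file is not prespecified in the plan.

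Four stronger readings are tempting, and the document does not support them.

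- A reader might infer that the 0.80 was miscalculated. Margins of about 22 to 28 points would produce it. The fault is missing specification, not a demonstrated arithmetic error.
- A reader might infer that the primary analysis is a test for a difference, with non-significance read as non-inferiority. The wording about a difference occurs only in a garbled power sentence; the hypothesis before it is correctly framed, and no primary test is named.
- A reader might infer that the increase of 10 per arm will be driven by fusion results. The surrounding text speaks of power and budget, and the Data and Safety Monitoring section does not mention comparing fusion by arm. The condition for the increase is undefined, so this is a possibility left open, not a plan.
- A reader might infer that a strict margin is unattainable at this size. Equal counts cannot meet 10 points with 18 per arm, but 18/18 on ViviGen against 17/18 on control would at one-sided 5%.

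It is also fair that 86% in both arms is one reading: the phrase about both arms may qualify only the dropout rate. No second rate is given on either reading.

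**Conclusion.** The concern holds as a missing decision rule and must be fixed. As written, the trial's only primary hypothesis cannot be decided, because margin and alpha are absent throughout. The 0.80 is undetermined rather than wrong, and it does not describe the planned enrolment.

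The absence of margin and alpha is a matter of text and needs no assumption. The sizes are illustrations: they rest on an assumed one-sided alpha of 5% or 2.5%, assumed margins, a true rate of 86% in both arms and 10% dropout. Across margins of 10 to 25 points, power at 40 enrolled never exceeds 0.66. To have 0.80 at 60, the plan would have to tolerate a fusion rate some 22 to 28 points lower, a tolerance the reader can neither see nor judge.

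**What to change.** Amend the Statistical Analysis section as follows.

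1. State a one-sided alpha and a clinically justified margin. Report the margin, alpha and test entered in PASS 15, but keep that margin only if it can be clinically justified. Fix both before any aggregate comparison of fusion by arm is made. Because the study is open-label and films are read at each visit, a condition that nobody has seen individual results may not be achievable.
2. Replace the power sentence with the non-inferiority power at that margin for 40 enrolled (36 evaluable) and for the optional 60 (54 evaluable). Low power, openly stated, is acceptable.
3. Add the rule: non-inferiority is concluded only if the lower one-sided score-type confidence limit for ViviGen minus control lies above minus the margin.
4. State that the optional 10 per arm is decided without any aggregate comparison of fusion by arm.
5. If no margin can be justified, drop the non-inferiority claim and report the difference with a score-type 95% CI, expected to be roughly 23 points either way at 18 per arm and 19 at 27 per arm.

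The cost is a text amendment through the IRB and retrieval of the PASS output. No extra patients, visits or data are needed. The drawback is that the stated power will look less favourable: about 0.52 to 0.66 at 40 if the margin was near 22 to 28 points, and about 0.11 to 0.36 if the justified margin is 10 to 15 points.
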